16.1.2. SERIOUS ADVERSE EVENTS AND DEATH

Serious adverse events are those events recorded as "Serious" on the Adverse Events page of the eCRF. SAEs will be listed and summarized by SOC and PT.

AEs leading to death are those events which are recorded as "Fatal" on the Adverse Events page of the (e)CRF. Deaths may also be recorded on the End of Treatment page and the Completion/Withdrawal from Study page of eCRF. A listing all deaths will be prepared based on these sources. A listing of all TEAEs leading to death will also be prepared.

16.1.3. EXTRAPYRAMIDAL TEAES

Extrapyramidal TEAEs will be defined by the Standard MedDRA Query (SMQ) labeled as Extrapyramidal Syndrome. The number and percentage of subjects with at least one TEAE PT mapped to an extrapyramidal term contained in the SMQ will be presented. In addition, the extrapyramidal terms will be summarized. Separate tables will be presented for the narrow and broad interpretation of the SMQ.

16.1.4. ABUSE-RELATED TEAES

TEAEs will be categorized as defined in the table below to monitor signals of potential abuse of ITI-007. The number and percentage of subjects with at least one abuse-related TEAE will be summarized by category and the applicable PTs below.

Table D: Abuse-Related PTs

| Category | Applicable Preferred Terms |
|---|---|
| Euphoria | Euphoric mood; Elevated mood; Feeling abnormal; Feeling drunk; Feeling of relaxation; Dizziness; Thinking abnormal; Hallucination; Inappropriate affect |
| Impaired attention, cognition, and mood | Somnolence; Sedation; Mood disorders and disturbances |
| Dissociative/psychotic | Psychosis; Aggression; Confusion and disorientation |
| Other related terms | Drug tolerance; Habituation; Drug withdrawal syndrome; |

Document: Author: ...\ITI\ITI-007\MYA11638\Biostatistics\Documentation\SAP\ITI-007-404 SAP Final V1.0 12JUN2019.docx

Version Number:1.0

Version Date: 12JUN2019

Page 33 of 53

| Substance-related disorders |
|-----------------------------|
| |

16.2. **LABORATORY EVALUATIONS**

Results from the central laboratory will be included in the reporting of this study for hematology, clinical chemistry, urinalysis and screening serology. A list of laboratory assessments to be included in the outputs is included in the protocol, Section 8.5. Summary statistics will be presented in standard international (SI) and US conventional units.

Quantitative laboratory measurements reported as "< X", i.e. below the lower limit of quantitation (BLQ), or "> X", i.e. above the upper limit of quantitation (ULQ), will be converted to X for the purpose of quantitative summaries, but will be presented as recorded, i.e. as "< X" or "> X" in the listings.

Blood samples for laboratory evaluations will be collected after an overnight fast (≥10 hours) during screening and on Days 8, 22, 43 and Day 57 safety follow-up or during the discontinuation visit. All non fasting results for glucose, insulin and triglycerides will be excluded from descriptive statistics but will appear in the data listings.

The following summaries will be provided for laboratory data:

- Actual and change from baseline by visit, and for last on-treatment assessment where applicable (for quantitative measurements)
- Incidence of abnormal values according to normal range criteria
- Shift from baseline according to normal range criteria (for quantitative measurements and categorical measurements)
- Shift from baseline according to markedly abnormal criteria defined in Section 16.2.1 (for quantitative measurements and categorical measurements)
- Listing of subjects meeting markedly abnormal criteria.
- Incidence of liver function related values meeting pre-defined criteria, as defined in Section 16.2.2, during the treatment period and the entire study

LABORATORY REFERENCE RANGES AND MARKEDLY ABNORMAL CRITERIA 16.2.1.

Quantitative laboratory measurements will be compared with the relevant laboratory reference ranges in SI units and US Conventional units and categorized as:

- o Low: Below the lower limit of the laboratory reference range.
- Normal: Within the laboratory reference range (upper and lower limit included).
- o High: Above the upper limit of the laboratory reference range.

In addition to the high and low quantitative laboratory assignments (as identified by means of the laboratory reference ranges), markedly abnormal quantitative safety (and other) laboratory assessments will also be identified in accordance with the predefined markedly abnormal criteria as presented in Table E:

Document: ...\ITI\ITI-007\MYA11638\Biostatistics\Documentation\SAP\ITI-007-404 SAP Final V1.0 12JUN2019.docx Author:

Version Number:1.0

STATISTICAL ANALYSIS PLAN: PROTOCOL ITI-007-404 Page 34 of 53

Markedly Abnormal Values for Laboratory Evaluations Table E:

| Hematology Parameter | Markedly Abnormal Range |
|-------------------------------------|----------------------------------|
| Hemoglobin | Male: ≤ 11.5 g/dL |
| | Female: ≤ 9.5 g/dL |
| Hematocrit | Male: ≤ 37% |
| | Female: ≤ 32% |
| White Blood Cell (WBC) Count | ≤ 2.8 x 10 ³ cells/µL |
| | ≥ 16 x 10 ³ cells/µL |
| Neutrophils (percent) | ≤ 15% |
| Eosinophils (percent) | ≥ 10% |
| Platelet Count | ≤ 75 x 10 ³ cells/µL |
| | ≥ 700 x 10 ³ cells/μL |
| Chemistry Parameter | Markedly Abnormal Range |
| Alkaline Phosphatase | ≥ 2 x ULN |
| Gamma-glutamyl transferase (GGT) | ≥ 3 x ULN |
| Alanine aminotransferase (ALT) | ≥ 3 x ULN |
| Aspartate aminotransferase (AST) | ≥ 3 x ULN |
| Total Bilirubin | ≥ 2 x ULN |
| Albumin | < 2.5 g/dL |
| Glucose | < 45 mg/dL |
| | > 160 mg/dL |
| Sodium | < 130 mmol/L |
| | > 150 mmol/L |
| Potassium | < 3 mmol/L |
| | > 5.5 mmol/L |

Document:

...\ITI\ITI-007\MYA11638\Biostatistics\Documentation\SAP\ITI-007-404 SAP Final V1.0 12JUN2019.docx

Author:

Version Number:1.0

| Page | 35 | of | 53 |
|------|----|----|----|
|------|----|----|----|

| Chloride | < 90 mmol/L |
|------------------------------|-------------------------|
| | > 115 mmol/L |
| Calcium | < 7 mg/dL |
| | > 12 mg/dL |
| Blood Urea Nitrogen | ≥ 30 mg/dL |
| Creatinine | ≥ 2.0 mg/dL |
| Creatine Phosphokinase (CPK) | ≥ 5 x ULN |
| HbA _{1c} | ≥ 7.5% |
| Prolactin | ≥ 5 x ULN |
| Total Cholesterol (fasting) | ≥ 300 mg/dL |
| LDL Cholesterol (fasting) | ≥ 200 mg/dL |
| Triglycerides (fasting) | ≥ 300 mg/dL |
| Urinalysis Parameter | Markedly Abnormal Range |
| RBC | > 10 cells/hpf |
| WBC | > 20 cells/hpf |

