4 STUDY DESIGN

This is a Phase 3, randomized, double-blind, placebo-controlled, multi-center study to evaluate the efficacy and safety of lumateperone monotherapy in the treatment of patients with major depressive episodes associated with Bipolar I or Bipolar II Disorder (Bipolar Depression). The study consists of the following periods: Screening Period, double-blind On-treatment Period, and Safety Follow-up Period.

Screening Period (2 Weeks)

Potential patients will be evaluated during a Screening Period lasting up to 2 weeks, to ensure sufficient washout of restricted medications. Extension to the screening period may be approved by the Sponsor or representative in extenuating circumstances related to the patient or caregiver.

After obtaining written informed consent, diagnostic interviews and physical examinations will be conducted, vital signs and ECGs will be assessed, and blood samples for laboratory assessments will be collected. Patients considered potentially eligible for participation will be required to discontinue their current antidepressant treatment and/or other psychotropic drugs.

At baseline (Visit 2), patients who continue to meet all eligibility criteria will be randomly assigned to 1 of the 2 treatment arms for a 6-week, double-blind treatment period. Patients will be randomly assigned to 1 of the following groups: 60 mg ITI-007 or matching placebo.

Double-Blind On-Treatment Period (6 Weeks)

Patients will take their first dose of study medication the evening of their baseline visit. A single dose will be taken each day in the evening, with or without food, for the duration of the 6-week On-treatment Period.

Following randomization, patients will attend the clinic on Days 8, 15, 22, 29, 36 and 43.

Safety Follow-up Period (2 Weeks)

A return to the clinic for a safety follow-up visit will occur at Week 8, approximately 2 weeks following the last dose of study medication. If possible, patients who withdraw prematurely will be seen for an early termination visit (within 1 week of early termination) and will be asked to return to the clinic for a safety follow-up visit 2 weeks following withdrawal.

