Patients who discontinue study or study drug due to AEs will be listed and summarized by system organ class and preferred term. TEAEs will be categorized to monitor signals of potential abuse of ITI-007 and the number and percentage of patients with at least one abuse-related TEAE will be summarized by the pre-specified categories.

Additional summaries of TEAEs will be presented as deemed necessary and will be specified in the SAP.

Laboratory assessments, including hematology and chemistry, vital signs and ECGs, will be listed and summarized by treatment group and visit. Summaries may include actual and change from baseline, incidence of abnormal values according to normal range criteria, shift from baseline to each visit according to markedly abnormal criteria, and listing of patients meeting certain abnormal criteria. Pre -specified chemistry results, including but not limited to blood levels of fasting glucose, total cholesterol, triglycerides, and insulin will be evaluated for whether there is a difference between ITI-007 and placebo. Any comparison between the treatment groups will be considered exploratory.

The observed and change from baseline in the scores of the different rating scales (YMRS, C SSRS, AIMS, BARS, and SAS) will be summarized by treatment group and visit.

Additional details for analyses on safety assessments will be provided in the SAP.

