16. SAFETY OUTCOMES

All outputs for safety outcomes will be based on the SAF Set.

16.1. FOR BY VISIT SUMMARIES OF CHANGE FROM BASELINE SUMMARIES, THE LAST VALUE ON TREATMENT (LAST ASSESSMENT ON OR BEFORE THE LAST DOSE OF STUDY MEDICATION PLUS ONE DAY) WILL BE PRESENTED. ADVERSE EVENTS

Adverse Events (AEs) will be coded using the Medical Dictionary for Regulatory Activities

Document: ...\ITI\ITI-007\MYA11638\Biostatistics\Documentation\SAP\ITI-007-404 SAP Final V1.0 12JUN2019.docx
Author: Version Number:1.0

Version Number:1.0
Version Date: 12JUN2019

Page 31 of 53

(MedDRA) central coding dictionary currently in effect at the time of analysis or database lock.

Treatment emergent adverse events (TEAEs) are defined as AEs that started or worsened in severity on or after the first dose of study medication and on or before the date last dose of study medication plus one day.

All AEs with an onset date after the last dose of study medication plus one day will be listed in the AE data listing and labelled as 'Follow-up Adverse Event'.

See APPENDIX 2 for handling of partial or completely missing dates for AEs. In the case where it is not possible to define an AE as treatment emergent or not due to missing dates, the AE will be classified as the worst case, i.e. treatment emergent.

An overall summary of number of subjects within each of the categories described in the subsections 16.1.1 and 16.1.2 below will be provided as specified in the TLF shells.

Listings will include all AEs, TEAEs and Non-TEAEs. A seperate listing for TEAEs leading to study discontinuation will be presented.

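### Table D counts drug withdrawal syndrome only among TEAEs, so about 14 of 15 off-drug days lie outside its count

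*SAP*

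**What the plan says.** SAP 16.1.4 gives the purpose of Table D: "TEAEs will be categorized as defined in the table below to monitor signals of potential abuse of ITI-007". Its last row contains "Drug tolerance; Habituation; Drug withdrawal syndrome". The counting rule is: "The number and percentage of subjects with at least one abuse-related TEAE will be summarized by category and the applicable PTs below". The safety part of Protocol 12.4.4 uses the same event base: "the number and percentage of patients with at least one abuse-related TEAE will be summarized by the pre-specified categories".

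Under SAP 16.1, a TEAE starts or worsens from the first dose onwards and "on or before the date last dose of study medication plus one day". Protocol 12.4.4 sets the same end point. For later events the SAP says: "All AEs with an onset date after the last dose of study medication plus one day will be listed in the AE data listing", where they carry a follow-up label. The visible text specifies no table for that group.

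Observation continues beyond the window. Protocol 4 states: "A return to the clinic for a safety follow-up visit will occur at Week 8, approximately 2 weeks following the last dose of study medication". Protocol 9.4 collects adverse events from consent until the patient's participation ends, so events in the follow-up period reach the database.

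**The concern.** Withdrawal from the study drug appears after doses stop. Table D names the withdrawal term as something to monitor, but applies an event window built for on-drug effects. The two weeks in which the design can best observe withdrawal fall almost wholly outside that window.

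What is at stake is how the row is read. A count of none or very few in both arms could be taken as reassurance when it may mostly reflect where the window ends. A patient listing does not replace the randomised comparison. New symptoms after Day 43 may come from stopping the drug or from the underlying illness, and the placebo arm is what separates the two.

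**Working it through.** The documents give no event count or rate for this table, so there is no planned figure to reproduce. The check is date arithmetic, followed by a range for what the documents leave open.

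**Inputs**
- Dosing: once daily in the evening (Protocol 4), at about 20:00 to 22:30 (Protocol 6.2).
- Completers: 42 days on treatment, with the Day 43 assessment after the last dose (SAP 7, Table A). The last planned dose is therefore taken as the evening of Day 42.
- TEAE window: ends on the calendar date of last dose + 1 (SAP 16.1).
- Follow-up visit: Day 57 ± 2 (Protocol contents list, 7.9).

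**Step 1: where the window closes.** Day 42 + 1 = Day 43, up to midnight. The first undosed evening is also Day 43.
- Hours after the last dose = (24:00 − dose time) + 24. This gives 4 + 24 = 28 h for a 20:00 dose and 1.5 + 24 = 25.5 h for a 22:30 dose.
- Hours after the first missed dose: 28 − 24 = 4 h, or 25.5 − 24 = 1.5 h.

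These hours hold for any patient with a recorded last dose in that evening slot, whatever the day.

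**Step 2: share of off-drug days covered.** Share = 1/(follow-up day − 42).

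| Follow-up day | Off-drug days | In window | Share |
|---|---|---|---|
| 55 | 13 | 1 | 7.7% |
| 57 | 15 | 1 | 6.7% |
| 59 | 17 | 1 | 5.9% |

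Measured in hours from the first missed dose to a midday visit, the share runs from 1.5/373.5 = 0.4% to 4/280 = 1.4%.

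**Step 3: share of events captured.** The share of days is not the share of events, and the documents give neither a half-life nor a withdrawal onset time. Assume exponential onset with mean m days. Then capture = (1 − e^(−w/m))/(1 − e^(−T/m)), where w is the time inside the window and T is the follow-up time, taken as 14.5 days from the last dose (13.5 from the first missed dose).

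| Clock starts at | m = 1 | m = 3 | m = 7 |
|---|---|---|---|
| First missed dose | 6% to 15% | 2% to 6% | 1% to 3% |
| Last dose | 65% to 69% | 30% to 33% | 16% to 18% |

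**Step 4: what a low count would mean.** Take 175 per arm (350/2) and an assumed true withdrawal rate of 5%, so 175 × 0.05 = 8.75 expected cases. With capture c, the expected count is 8.75c and the chance of a zero count is (1 − 0.05c)^175.

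| Capture c | Expected count | Chance of zero |
|---|---|---|
| 1% | 0.09 | 92% |
| 6.7% | 0.58 | 56% |
| 30% | 2.62 | 7% |

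At low capture, zero is the likely result even with a real effect. At high capture it is not.

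**Step 5: other SAP outputs.** C-SSRS suicidality is summarised by treatment and post-treatment period (SAP 16.6.5), hypnotic use also for post treatment (SAP 13), and liver criteria over the entire study (SAP 16.2). Off-drug summaries are therefore already part of this plan; adverse events are treated differently.

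**The case against.** A reader might infer that the row will be about zero in both arms whatever the drug does. The documents do not support that. Events after doses missed during treatment can count, as can onset within about 28 hours of the last dose, and events that cannot be dated default to treatment emergent (SAP 16.1). Patients also stop prior psychotropics before baseline, so a withdrawal reaction to those drugs that begins after the first dose would enter in either arm. Step 3 reaches 69% capture under very early onset.

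A reader might also infer that the off-drug period is missing from every adverse event table. That goes too far. SAP 16.1.2 summarises serious events and SAP 16.1.1 summarises events leading to study withdrawal, neither limited to TEAEs. The gap is in non-serious events.

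Nor is Table D as a whole at fault. The euphoria, cognition and psychotic rows describe effects expected on drug, and the TEAE window suits them.

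Protocol 12.4.4 also promises summaries of reported and observed adverse events by group and visit, named apart from TEAEs. That general promise does not override the SAP's specific rule that later events are listed, and Protocol 12.4 lets the SAP depart from the default summaries.

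Two further points stand. The protocol and SAP agree with each other, so there is no contradiction. The table shells were not supplied and parts of the SAP are blacked out, so a follow-up event table may exist out of sight.

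**Conclusion.** The concern holds for the withdrawal term only. As written, the TEAE rule leaves about 14 of 15 off-drug days (12 of 13 to 16 of 17) outside the count, and non-serious withdrawal events in those days enter no by-arm table specified in the visible text. A low count in this row therefore cannot show absence of a withdrawal signal.

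The day count assumes a last dose on the evening of Day 42 and a recorded last-dose date. If a discontinued subject's end date is missing, SAP 14 substitutes the last dispense date, which can close the window earlier still. The share of events lost depends on onset timing that the documents do not give. The primary and key secondary analyses are unaffected. This is a cheap reporting improvement that makes one planned safety row interpretable.

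**What to change.** Keep the TEAE definition, the existing Table D counts and the adverse event listing.

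- **SAP 16.1.4:** add a separate by-arm count of withdrawal-related terms (at least drug withdrawal syndrome) with onset after the last dose date plus one day, through the follow-up visit. Starting there avoids overlap with the TEAE column on Day 43. Use subjects with any post-treatment follow-up as the denominator, and show that number by arm.
- **SAP 16.1:** add one by-arm table of follow-up adverse events by system organ class and preferred term.

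The cost is SAP wording and one or two descriptive tables from data already collected. The main limit is that follow-up may be less complete in early withdrawals: Protocol 2.2 calls the visit mandatory, Protocol 4 only asks premature withdrawals to return, and SAP 4.1 describes the period for those who completed treatment.

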8.5 Laboratory Procedures/Evaluations

8.5.1 Clinical Laboratory Evaluations

Blood and urine samples collected from patients will be forwarded to a central laboratory for analysis. Further details regarding sample collections, processing and specific testing can be found in the study reference manual.

All samples for clinical laboratory analysis will be collected after an overnight fast (≥10 hours), after any scheduled ECG or vital signs have been recorded, and prior to dosing with study treatment. Samples for clinical laboratory analysis will be used only for the evaluation of safety and tolerability.

Any abnormal laboratory test results (hematology, clinical chemistry, or urinalysis) or other safety assessments (e.g., ECGs, vital sign measurements), including those that worsen from baseline, felt to be clinically significant, in the medical and scientific judgment of the investigator, are to be recorded as AEs or SAEs.

However, any clinically significant safety assessments that are associated with the underlying disease, unless judged by the investigator to be more severe than expected for the patient's condition, are not to be reported as AEs or SAEs.

The following clinical analytes will be determined:

Hematology: hematocrit; hemoglobin; HbA_{1c} (only at screening V1 and end of study treatment V8); red blood cell count with indices (mean corpuscular volume, mean corpuscular hemoglobin, and mean corpuscular hemoglobin concentration); reticulocytes; white blood cell count and differential (neutrophils, lymphocytes, monocytes, eosinophils, and basophils) reported as percent (%) and absolute values; and platelets (platelet count, prothrombin time and partial thromboplastin time).

Clinical chemistry: albumin; alkaline phosphatase; blood urea nitrogen; gammaglutamyl transferase; calcium; creatinine; glucose; insulin; cholesterol (high-density lipoprotein and low-density lipoprotein [LDL] [calculated] and homogenous LDL will be reported, and homogenous LDL will be reflexed if a patient's triglycerides are >400); triglycerides; phosphate; potassium; prolactin; ALT; AST; lactate dehydrogenase; sodium; chloride; bilirubin (total, direct); total protein; uric acid; creatine phosphokinase; and thyroid panel (at screening only, thyroid-stimulating hormone will be assayed and if the result is abnormal, the free thyroxine and free triiodothyronine will be assayed).

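### SAP Table E has no absolute neutrophil criterion: a count just above 0.42 x 10³/µL can escape the markedly abnormal class while one near 2.4 falls into it

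*SAP*

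**What the plan says.** Three rules in SAP 16.2.1, Table E, bear on this point:

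- Neutrophils, low side only: "Neutrophils (percent) | ≤ 15" percent.
- White cells, low side: "White Blood Cell (WBC) Count | ≤ 2.8 x 10 ³ cells/µL".
- White cells, high side: "≥ 16 x 10 ³ cells/µL".

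The row that opens "Neutrophils (percent" is the only neutrophil row. Table E has no row for the absolute neutrophil count and no rule that combines white cells with the differential.

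The absolute count is available. Protocol 8.5.1 has the white-cell differential "reported as percent (%) and absolute values", and SAP 16.2 takes its tests from there: "A list of laboratory assessments to be included in the outputs is included in the protocol, Section 8.5".

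Table E drives two outputs named in SAP 16.2. One is described as "Shift from baseline according to markedly abnormal criteria defined in Section 16.2.1"; the other is the listing of subjects who meet the criteria. Separately, SAP 16.2.1 sorts every quantitative result into low, normal or high against the laboratory's reference range.

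**The concern.** The number of circulating neutrophils is white cells times the neutrophil fraction. Limits placed on each factor separately do not limit the product in a sensible order: two values that each sit just inside their limits can multiply to a very low count, and a low fraction of a high white count can give a much higher one. The stated rule can therefore class the higher of two absolute counts as markedly abnormal and leave out the lower.

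The choice of percent is not explained. Table E judges white cells and platelets by absolute count. The SAP also combines measurements where one alone is not enough, as in the Hy's Law rule (16.2.2, Table F) and the paired level-and-change rules for vital signs (16.4.1, Table H).

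At stake is who appears, by arm, in the planned display of marked laboratory outliers.

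**Working it through.** The plan states no absolute neutrophil figure, so there is nothing to reproduce. The check is direct arithmetic.

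**Inputs.** Neutrophil limit 15% or less, and white-cell limits 2.8 or less and 16 or more (x 10³/µL), all from SAP Table E. Assumption: the laboratory's absolute count equals white cells times percent, apart from rounding.

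**Formula.** Absolute neutrophil count (ANC) = white cells x percent / 100. A result escapes both rules when white cells lie strictly between 2.8 and 16 and neutrophils are above 15%.

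**Lower bound of unclassed counts.** 2.8 x 0.15 = 0.42 x 10³/µL. It is approached but not reached, because both rules include equality.

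| White cells (10³/µL) | Neutrophils (%) | ANC (10³/µL) | Markedly abnormal under Table E? |
|---|---|---|---|
| 2.9 | 16 | 0.46 | no |
| 3.0 | 20 | 0.60 | no |
| 4.0 | 16 | 0.64 | no |
| 15.9 | 15 | 2.39 | yes, by the percent rule |

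If white cells are reported to 0.1 and percent to whole numbers, 0.46 is the lowest count that escapes.

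**Ordering.** 0.464 / 2.385 = 0.19. The unclassed count in the first row is about one fifth of the classed count in the last. This reversal does not depend on any cut-off for the absolute count.

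**Width of the gap.** The documents give no absolute cut-off, so three illustrative values are used, with neutrophils just above 15%. The highest white count at which the ANC stays below the cut-off is cut-off / 0.15:

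- 0.5: 0.5 / 0.15 = 3.33
- 1.0: 1.0 / 0.15 = 6.67
- 1.5: 1.5 / 0.15 = 10.0

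How often such values would occur cannot be worked out from the documents.

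**The case against.** The strongest reply is that Table E is an added layer, and a very low count would be seen without it. Most of this stands.

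- **By-visit summaries.** SAP 16.2 summarizes actual values by visit, and SAP 8 includes the minimum by default. The value would be the minimum for its arm and visit, provided it is the assessment selected for that window under SAP 7.
- **Normal-range tables and listings.** The value counts as low if it lies below the laboratory's range, which the documents do not give, and it appears in the source listings. Protocol 12.4.4 also provides for marking out-of-range values where appropriate.
- **Clinical routes.** Protocol 8.5.1 has results that the investigator judges clinically significant recorded as adverse events, with an exception for those tied to the underlying disease. Protocol 10.1 provides regular blinded review of laboratory outliers.

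A reader might therefore infer too much: that marked neutropenia would go undetected, or that Table E is the trial's only means of finding hematological toxicity. The documents do not support either. Nor do they define a neutropenia grade, so they cannot show that 0.46 is severe or that 2.4 is normal.

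It can also be said that percent is a legitimate convention for a descriptive screen; eosinophils are judged that way too. That is fair, and it is why the percent row need not be removed.

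The other routes do not close the gap, however. A minimum does not give the number of patients affected or their shift from baseline. The low category does not separate a value just under the range from one near 0.46. The clinical routes rest on judgment, and Protocol 10.1 states no neutrophil criterion. SAP 16.2.1 itself adds the markedly abnormal class on top of low and high.

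**Conclusion.** The point holds as a limited gap in one descriptive safety display. Under Table E, an absolute neutrophil count down to just above 0.42 x 10³/µL can escape the markedly abnormal class while a count of about 2.4 is placed in it. The loss is the patient's entry in the markedly abnormal shift table and in the subject listing.

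The arithmetic rests only on the limits in Table E and on the absolute count being the product of white cells and percent. The clinical meaning of any particular count is left open, because the documents do not settle it. Efficacy, power, error rate and analysis sets are untouched.

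**What to change.** Add a row for the absolute neutrophil count to Table E, next to the percent row, and use it in the markedly abnormal shift table and listing. The sponsor's safety team should choose the reporting cut-off and fix it before unblinding. It is a threshold for display, not a rule for managing patients.

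The cost is one more row of output. The absolute count is already collected, and Protocol Section 12 allows changes to analysis methods to be documented in the SAP without a protocol amendment. If treatment codes have already been opened, the same listing can be produced and labelled post hoc.
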